### **3.2** Secondary Objectives

To estimate progression-free survival (PFS) for M7824 in patients with:

• MSI-H solid tumors whose disease has progressed on prior immune checkpoint blockade therapy (Cohort A-C).

OR

Treatment-refractory, CMS4 mCRC coadministered SBRT (Cohort B). While SBRT is preferred, IMRT or 3D conformal techniques may be utilized at the discretion of the treating radiation oncologist depending on the dose to surrounding normal tissues. Patient will receive a total dose of 24Gy over three days with one of the following modalities, at the discretion of the treating radiation oncologist: SBRT, IMRT and 3D conformal.

To estimate overall survival (OS) for M7824 in patients with:

• MSI-H solid tumors who are refractory to prior immune checkpoint blockade therapy (Cohort A-C).

OR

Treatment-refractory, CMS4 mCRC coadministered SBRT (Cohort B). While SBRT is preferred, IMRT or 3D conformal techniques may be utilized at the discretion of the treating radiation oncologist depending on the dose to surrounding normal tissues. Patient will receive a total dose of 24Gy over three days with one of the following modalities, at the discretion of the treating radiation oncologist: SBRT, IMRT and 3D conformal.

OR

ctDNA(+) resected mCRC following completion of standard-of-care therapy (Cohort D).

To estimate disease-free survival (DFS) in patients with resected mCRC following standard-of-care treatment (cohort D).

To evaluate safety and tolerability of treatment with M7824 in patients with:

• MSI-H mCRC who are refractory to prior immune checkpoint blockade therapy (Cohort A-C).

OR

• Treatment-refractory, CMS4 mCRC (Cohort B)

OR

.

ctDNA(+) resected mCRC following completion of standard-of-care therapy (Cohort D).

### **3.3 Exploratory Objectives**

1. To evaluate intratumoral pharmacodynamic changes in immune populations using paired biopsies from patients with MSI-H solid tumors (Cohort A-C) or CMS4 mCRC treated with

M7824 and SBRT (Cohort B). While SBRT is preferred, IMRT or 3D conformal techniques may be utilized at the discretion of the treating radiation oncologist depending on the dose to surrounding normal tissues. Patient will receive a total dose of 24Gy over three days with one of the following modalities, at the discretion of the treating radiation oncologist: SBRT, IMRT and 3D conformal.

2. To characterize circulating immune cell populations and cytokine profiles in tumor and circulation following treatment with M7824.

3. To describe changes in levels of TGF- $\beta$  following treatment with M7824.

4. To correlate the presence of microsatellite instability with CMS1 profile.

5. To correlate MSI-H and CMS4 to CpG island methylator phenotype (CIMP) status, KRAS and BRAF mutation status.

6. To quantify correlation with CMS4 and immune populations within tumor infiltrate.

7. To correlate anti-tumor response to M7824 with PD-L1 expression.

8. To conduct RNAseq, RNA Scope, WES targeted sequencing and tissue IO gene expression by Nanostring.

9. To evaluate novel markers in blood by liquid biopsy including, but not limited to, circulating-free DNA (cfDNA), exosomes, and circulating tumor cells (CTC).

10. To describe changes in microbiome profiling upon treatment with M7824 (with or without radiation).

#### 4 Investigational Plan

#### 4.1 Overall Trial Design and Plan

#### 4.1.1.1 Cohort A-C – MSI-H solid tumors

This is a phase Ib expansion study to assess efficacy of M7824 in patients with MSI-H solid tumors who have progressed on prior anti-PD-1/PD-L1 therapy. The hypothesis is that these patients will demonstrate anti-tumor response upon treatment with M7824. Patients successfully enrolled will have had at least two doses of prior immune checkpoint therapy (anti-PD1, anti-PDL1 or anti-CTLA4) with documented progression on CT or MRI imaging.

M7824 will be administered intravenously at a dose of 1200mg every 14 days (-3/+1 day). M7824 will be administered until documented PD, unacceptable toxicity, or withdrawal of informed consent. Tumor assessments will be performed every 8 weeks. Progressive disease, stable disease, partial response, and complete response will be defined by iRECIST 1.1. Patients who discontinue due to toxicity will continue to be assessed via imaging until documented PD.

### 4.1.1.2 Cohort B – CMS4 mCRC

This is a phase 2, single arm, Simon's optimal two-stage design to assess ORR in treatmentrefractory CMS4 mCRC receiving M7824 with SBRT. The hypothesis is that efficacy of M7824 coadministered with SBRT will be demonstrated in patients with CMS4 mCRC

Patients successfully enrolled will have had CMS4 classification after characterization of their pretreatment primary tissue biopsy. M7824 will be administered intravenously at a dose of 1200mg every 14 days (+/- 7 days). The first dose of M7824 will be administered alone. After the second dose of M7824, patients will receive SBRT for a total dose of 24Gy over three days, with first treatment of radiotherapy administered within 7 days of completion of the second dose of M7824 (cycle 1, day 15). Radiotherapy must be completed prior to the third dose of M7824. While SBRT is preferred, IMRT or 3D conformal techniques may be utilized at the discretion of the treating radiation oncologist depending on the dose to surrounding normal tissues. Patient will receive a total dose of 24Gy over three days with one of the following modalities, at the discretion of the treating radiation oncologist: SBRT, IMRT and 3D conformal.

M7824 will be continued until documented PD or unacceptable toxicity. Tumor assessments will be performed every 8 weeks. Progressive disease, stable disease, partial response, and complete response will be defined by iRECIST 1.1. Patients who discontinue due to toxicity will continue to be assessed via imaging until documented PD.

# 4.1.1.3 Cohort D – ctDNA(+) MSS mCRC following resection of metastatic disease

This is a pilot study to assess the clearance of ctDNA with M7824 following R0 resection of metastatic disease in patients with MSS mCRC. Patients with oligometastatic colorectal cancer must have undergone an R0 resection with no remnant clinically or radiographically evident disease. The primary tumor must have also been resected, and patients must have completed all standard-of-care treatment for the primary tumor (e.g., chemoradiation for primary rectal cancer, adjuvant chemotherapy, etc) at the discretion of the treating physician.

Following at least 14 days of completion of standard therapy, patients will be tested for the presence or absence of ctDNA. Patients with a confirmed (+) ctDNA result will be allowed to proceed with M7824 treatment.

M7824 will be administered intravenously at a dose of 1200 mg every 14 days (+/- 7 days). ctDNA and CT scans will be repeated at 12 weeks. Patients without evidence of clinical or radiographic progression will have the option to continue on treatment every 2 weeks with M7824, until the time of disease recurrence and/or progression, either radiographically or clinically. Radiographic assessments will occur every 12 weeks thereafter, until disease progression or patient discontinuation on study.

### 4.1.2 Planned number of subjects

### 4.1.2.1 Cohort A-C – MSI-H solid tumors

The planned number of subjects for this trial is 15 patients with MSI-H metastatic solid tumors.

### 4.1.2.2 Cohort B – CMS4 mCRC

In this Simon two-stage design, the planned number of subjects is 15 in the first stage. Should at least 2 patients demonstrate radiographic response (i.e. CR + PR), then 14 additional patients will be treated in the second stage, for a total of 29 patients. If there is an anti-tumor signal in the 29 patients with CMS4 metastatic CRC who are treated with this combination, then the study may be amended to expand patient selection across all CMS subgroups.

# 4.1.2.3 Cohort D -- ctDNA(+) MSS mCRC following resection of metastatic disease

The planned number of subjects for this cohort is 15 patients.

#### 4.1.3 Planned treatment duration

The trial duration for a subject is estimated to be up to 2 years. This includes an 28-day screening period (decision will be made in this period for subject's trial inclusion if all eligibility criteria are met), a treatment duration until confirmed PD, unacceptable toxicity, or any criterion for withdrawal from the trial or IMP occurs (see Section 4.5) and an 28-Day Safety Follow-up visit 4 weeks after the last dose of M7824 administration.

Subjects who have experienced a durable, confirmed PR or CR may continue treatment for a maximum of 12 months, although additional treatment is possible. If the Investigator believes that a subject may benefit from treatment beyond 12 months, it may be permissible after discussion with the principal investigator. In the case of pseudoprogression, subjects should continue treatment through one additional tumor assessment, if they meet the criteria described in Section 4.5.1.

Adverse events (AEs) and adverse drug reactions (ADRs) should be followed until they resolve, return to baseline, or are irreversible (see Section 6.1.4 for details).

In both cohorts, it is anticipated to enroll the first planned subject by October 2017, and the final subject enrolled by October 2018.

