#### 5.5.3.3 Immune-Related Adverse Events

For reporting irAE severity/toxicity grading, refer to CTCAE v4.03 toxicity grading system.

For treatment management of irAE per CTCAE v4.03 criteria, refer to American Society of Clinical Oncology (ASCO) Clinical Practice Guidelines and National Comprehensive Cancer Network irAE Management Guidelines.

Treatment of irAEs is mainly dependent upon severity as defined by NCI-CTCAE v4.03. In general, management by CTCAE v4.03 grading, as per ASCO, is listed below:

- Grade 1: study treatment should be continued with close monitoring, with the exception of some neurologic, hematologic, and cardiac toxicities.
- Grade 2: study treatment may be suspended for most Grade 2 toxicities, with consideration of resuming when symptoms revert to Grade 1 or less. Corticosteroids may be administered (initial dose of 0.5 to 1 mg/kg/day of prednisone or equivalent).
- Grade 3: study treatment is generally suspended and the high-dose corticosteroids (prednisone 1 to 2 mg/kg/day) or methylprednisolone 1 to 2 mg/kg/day) treatment should be initiated. Corticosteroids should be tapered over the course of at least 4 to 6 weeks. Some refractory cases may require infliximab or other immunosuppressive therapy.
- Grade 4: in general, permanent discontinuation of study treatment is recommended, with the exception of endocrinopathies that have been controlled by hormone replacement.

Since inhibition of PD-L1 stimulates the immune system, irAEs may occur. Treatment of irAEs is mainly dependent upon severity (NCI-CTCAE grade):

- Grade 1 to 2: treat symptomatically or with moderate dose steroids, more frequent monitoring
- Grade 1 to 2 (persistent): manage similar to high grade AE (Grade 3 to 4)
- Grade 3 to 4: treat with high dose corticosteroids

Treatment of irAEs should follow guidelines set forth in the ASCO/NCCN Management of Immunotherapy-Related Toxicities (https://www.nccn.org/professionals/physician\_gls/pdf/immunotherapy.pdf).

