### 6.1.3 End of Treatment

### 6.1.3.1 End of Treatment Visit

All subjects must undergo an End-of-Treatment visit after discontinuation of M7824 for any reason. This visit should be performed on the day of or within 7 days after the decision to discontinue trial treatment but before any new antineoplastic therapy is started (if possible), whichever occurs earlier (see **Tables 1-3**). If it is known to the Investigator at the time of the End of-Treatment visit that the subject will start new treatment within 28 days of last treatment or they will be unable to return within 28 days of last treatment, assessments associated with the 28-Day Safety Follow-up visit may be conducted at the End-of-Treatment visit. For all these subjects, the discontinuation visit consists of:

- Documentation of AEs and concomitant medication.
- Physical examination including vital signs and body weight.
- Eye signs and symptoms should be checked. If clinically relevant findings then an appropriate ophthalmology examination including slit lamp evaluation inclusive of the anterior segment and with visual acuity should be obtained within 2 days.

- Dermatological assessments (assessments for skin lesions or rash with biopsy of suspicious lesions).
- Laboratory hematology, full serum chemistry, and basic urinalysis.
- ECOG performance status will be assessed.

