#### 6.1.4.2 Long-term Follow-up / Trial Termination

All SAEs ongoing at the 28-Day Safety Follow-up visit must be monitored and followed up by the Investigator until stabilization or until the outcome is known, unless the subject is documented as "lost to follow-up." In addition, all trial drug-related SAEs occurring after 28-Day Safety Follow-up visit and ongoing at the Safety Follow-up visit have to be followed up in the same manner.

Subjects without PD at the 28-Day Safety Follow-up visit will be followed up for disease progression (CT / MRI scans every 12 weeks) until PD.

After the 28-Day Safety Follow-up visit, subjects will be followed quarterly ( $\pm$  14 days) for survival (including assessment of any further anticancer therapy). The survival follow-up will continue until 1 year after the last subject receives the last dose of M7824.

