## 6.4.1.5 Monitoring of Subjects with Adverse Events

Adverse events are recorded and assessed continuously throughout the trial (see Section 6.4.1.3) and are assessed for final outcome at the End of Treatment visit. After the End of Treatment visit only AEs that are deemed attributable to trial drug by the Investigator should be documented until the Safety Follow-up visit.

All SAEs ongoing at the 28-Day Safety Follow-up visit must be monitored and followed up by the Investigator until stabilization or until the outcome is known, unless the subject is documented as "lost to follow-up". In addition, all trial drug related SAEs occurring after 28-Day Safety Follow-up visit and ongoing at the Safety Follow-up visit must be followed up in the same manner.

Reasonable attempts to obtain this information must be made and documented. It is also the responsibility of the Investigator to ensure that any necessary additional therapeutic measures and follow-up procedures are performed.

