## 7.3.2 Secondary Endpoints

The secondary endpoints to this study are:

- PFS according to iRECIST 1.1 criteria.
- DFS (cohort D)
- OS
- Number, severity, and duration of treatment related AEs according to NCI-CTCAE v4.03

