### 7.5 Description of Statistical Analyses

#### 7.5.1 General Considerations

All data recorded during the study will be presented in individual data listings performed on the Safety Analysis Set. All data will be evaluated as observed, and no imputation method for missing values will be used. All data will be presented in a descriptive manner. Each cohort will be analyzed separately, and no multiplicity adjustment across cohorts will be performed.

Descriptive statistics will be used to summarize the trial results, that is, statistics for continuous variables may include means, medians, ranges, and appropriate measures of variability. Categorical variables will be summarized by counts and percentages. The uncertainty of estimates will be assessed by confidence intervals. Unless otherwise specified, the calculation of proportions

will be based on the sample size of the analysis set of interest. Counts of missing observations will be included in the denominator and presented as a separate category.

All other statistical analyses will be performed using SAS® Version 9.1.3 or higher, or R, Version 2.10.1 or higher.

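### The plan's sections disagree on how long non-serious related AEs are followed, so the secondary endpoint of related-AE duration can be truncated at about 28 days after the last dose

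*Combined protocol and SAP*

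**What the plan says.** **Follow-up to outcome.** Section 4.1.3 sets a general rule without limiting it to serious events: "Adverse events (AEs) and adverse drug reactions (ADRs) should be followed until they resolve, return to baseline, or are irreversible". It leaves the particulars to 6.1.4. In 6.1.4, the only rule that follows events to an outcome is in 6.1.4.2: "All SAEs ongoing at the 28-Day Safety Follow-up visit must be monitored and followed up by the Investigator until stabilization". It adds drug-related SAEs that arise later. It describes the quarterly contacts as being for survival and further anticancer therapy. Section 5.10 promises follow-up for AEs, but refers back to 6.1.4.

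**Time of final outcome.** Section 6.4.1.5 says that AEs "are assessed for final outcome at the End of Treatment visit". From then until the Safety Follow-up visit, only AEs attributed to the drug are documented. The AE footnotes of Tables 1-3 repeat this. The safety visit is 28 ± 5 days after the last dose (6.1.4.1).

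**Longer periods elsewhere.** All three schedules mark AE documentation at the 3-monthly long-term contacts; in Table 3 the mark carries note s, up to one year after discontinuation. Section 6.4.1.3 opens with a reporting period of 90 days after the last dose, then ends it at the 28-day visit.

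**Endpoint and analysis.** Section 7.3.2 lists as a secondary endpoint: "Number, severity, and duration of treatment related AEs according to NCI-CTCAE v4.03". Section 7.5.1 adds: "All data will be evaluated as observed, and no imputation method for missing values will be used". Sections 7.5.3.1 and 7.5.3.3 describe AE summaries but give no method for duration and no rule for events still open. Section 7.5.3.2 gives Kaplan-Meier with the percentage censored for time-to-event data, without naming AE duration.

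**The concern.** A duration needs an end date. Section 4.1.3 would supply one, or a finding that the event is irreversible, for every AE. Sections 6.1.4.2 and 6.4.1.5 would supply one after the safety visit only for SAEs. Site staff cannot tell from the text which rule applies to a non-serious related AE that is still open at that visit.

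Such events are foreseen. Section 6.4.1.4 has a reporting route for non-serious AEs of special interest at Grade 1-2 and at Grade 3 or above. Section 2.1.1 reports related Grade 1-2 hypothyroidism and hyperthyroidism in two subjects each.

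If the short rule is followed and data are taken as observed, an open event either enters with its duration cut at the visit or drops out as missing. Both lower the reported duration, and the longest events lose most. If cohorts or staff apply different rules, the observable durations are also not comparable: Table 3 leaves toxicity assessment unmarked at the 3-monthly contacts, while Tables 1 and 2 mark it.

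**Working it through.** The plan gives no figure for AE duration, so there is nothing to reproduce. The check has two steps.

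**Step 1: how long a non-serious related AE starting at the last dose can be observed, by governing text.**

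| Text taken as governing | Last point at which an end date is recorded |
|---|---|
| 6.4.1.5 and AE footnotes, with 6.1.4.1 | day 23-33 (28 ± 5) |
| 6.4.1.3, closing definition | day 21-35 (28 ± 7) |
| 6.4.1.3, opening definition | day 90 |
| Long-term AE rows of Tables 1-3 (Table 3 note s) | up to one year after discontinuation |
| 4.1.3 | resolution, baseline or irreversibility |

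These cannot all hold. The documents offer one indication that a 28-day window may be short: for Grade 3 immune-related AEs, "Corticosteroids should be tapered over the course of at least 4 to 6 weeks", that is, 28 to 42 days or more. This is a length of steroid treatment, not of the event, so it is used only as an order of magnitude.

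**Step 2: illustration of size.** These assumptions are not from the documents: durations are exponential with mean m, the event starts at the last dose, and observation stops at day c.

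- Share still open at c: exp(-c/m).
- Mean observed duration, with open events cut at c: m × (1 - exp(-c/m)).

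| m (days) | c (days) | Share open | Mean observed (days) |
|---|---|---|---|
| 42 | 28 | exp(-28/42) = 51% | 42 × (1 - 0.513) = 20.4 |
| 42 | 90 | exp(-90/42) = 12% | 42 × (1 - 0.117) = 37.1 |
| 84 | 28 | exp(-28/84) = 72% | 84 × (1 - 0.717) = 23.8 |
| 84 | 90 | exp(-90/84) = 34% | 84 × (1 - 0.343) = 55.2 |

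If open events are dropped instead of cut, the mean of the resolved events is m - c × exp(-c/m)/(1 - exp(-c/m)). For m = 42 and c = 28 this is 42 - 28 × 0.513/0.487 = 12.5 days. With c = 365 the cut means are 42.0 and 82.9 days, so the loss is close to nil.

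Censoring alone does not fully solve the problem. The exponential median is m × ln 2, which is 29.1 days for m = 42 and 58.2 for m = 84. Both lie beyond day 28, so a Kaplan-Meier median for these events would typically not be reached in a 28-day window.

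An event that starts before the last dose has a longer window and loses less; one that starts later loses more.

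**The case against.** The strongest reply is that the documents can be read as providing longer follow-up. AE documentation is marked in long-term follow-up in all three schedules, 6.4.1.3 opens with 90 days, 5.10 mentions AEs, and 6.4.3 follows clinically significant laboratory abnormalities until normal, chronic or stable. Section 7.5.3.2 already provides Kaplan-Meier with censoring. The endpoint is descriptive, in cohorts of 15, up to 29, and 15, and no decision uses it: the stopping rule in 7.6 counts patients with related Grade 3 or higher events, not their durations.

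Much of this stands. Truncation is not a settled consequence; it depends on which text governs. But the longer readings do not remove the conflict. The tables' own AE footnotes stop at the safety visit, 6.4.1.3 contradicts itself, 5.10 refers back to 6.1.4, and 6.4.3 covers laboratory values only. Section 7.5.3.2 does not name AE duration and stands under exploratory endpoints.

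Three stronger readings are tempting but unsupported:

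- **Only SAEs are followed once treatment ends.** A reader might infer this from the final-outcome wording together with the timing of the End of Treatment visit ("This visit should be performed on the day of or within 7 days after the decision to discontinue trial treatment"), and so assume a window of at most 7 days. The next sentence of 6.4.1.5 keeps documenting drug-attributable AEs, serious or not, to the safety visit. These are the events the endpoint counts.
- **Severe immune-related events are hit hardest.** Clinical Grade 4-5 events must be reported as SAEs (6.4.1.1), and so must events that cause hospitalisation (6.4.1.1.1). SAEs are followed to outcome.
- **A related Grade 3 event always leads quickly to an End of Treatment visit.** Section 4.1.4.2 requires discontinuation for most such events, whereas 5.5.3.3 says treatment is generally suspended. A suspended subject need not have that visit.

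**Conclusion.** The inconsistency is real and affects a listed secondary endpoint. It is confined to non-serious related AEs still open at the last documented visit. SAEs, events that end before that visit, and the number and severity parts of the endpoint are not cut short by it.

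If 6.1.4.2 and 6.4.1.5 govern, the mean observed duration of events starting at the last dose falls by roughly half for a true mean of 42 days (20.4/42 = 49%) and to 28% for a true mean of 84 days (23.8/84). If the 90-day period governs, 88% and 66% are retained (37.1/42 and 55.2/84). With a year of recording almost nothing is lost. These figures rest on the assumed exponential shape, the assumed means and onset at the last dose; they show scale and are not forecasts. How many events are affected cannot be derived from the documents.

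The point is worth correcting before data are collected, because end dates that were never recorded cannot be recovered by analysis. It does not touch the primary endpoints or the toxicity stopping rule.

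**What to change.** 1. Reconcile 4.1.3, 6.1.4.2, 6.4.1.3, 6.4.1.5 and the AE rows and footnotes of Tables 1-3. Non-serious treatment-related AEs open at the Safety Follow-up visit should have their end date or current status recorded at the long-term contacts already scheduled, until they meet one of the three end conditions in 4.1.3 or follow-up ends. Give 6.4.1.3 a single reporting period, and widen the stated purpose of the quarterly contacts in 6.1.4.2.
2. Remove the statement in 6.4.1.5 and the table footnotes that final outcome is assessed at End of Treatment.
3. State in 7.5.3.1 that duration of related AEs is summarised by the Kaplan-Meier method already described in 7.5.3.2, with events still open censored at the last assessment.

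Steps 1 and 3 are both needed: censoring avoids treating a cut duration as complete, but it cannot show durations beyond the last assessment.

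**Cost.** Amendment wording and one status/end-date field at existing contacts; no new visits. The main downside is precision: an event that resolves between quarterly contacts may have an end date known only to within about three months. Reported durations may also become longer.
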